6.2 Definition of Dose-Limiting Toxicities

A DLT is defined as the occurrence of any of the following events, within the first cycle of treatment, that are considered to be at least possibly related to OBI-888. All AEs unless they have been determined to be not related to study drug will be taken into consideration in determining DLTs. NCI-CTCAE version 4.03 will be the basis for the descriptive terminology and grading of AEs.

DLTs are defined as:

- Grade 4 neutropenia
- *Erade 3 febrile neutropenia with or without infection*
- Grade 4 thrombocytopenia or Grade 3 thrombocytopenia with bleeding
- ≥Grade 3 nausea and vomiting or diarrhea for more than 72 hours despite optimal supportive care
- Any other ≥Grade 3 non-hematological AE that does not resolve before the next infusion.

The DLT evaluation period is the first cycle; 28 days from start of study treatment.

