8.2.2 Regimen

OBI-888 will be administered as an IV infusion on Days 1, 8, 15, and 22 of each 28-day cycle in Part A and Part B of the study.

Treatment will continue until progressive disease, unacceptable toxicity, or decision by the Investigator or patient to discontinue treatment.

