8.3 Dose Modifications and Toxicity Management

Escalation to higher OBI-888 dose cohort is not permissible during the study.

Dose modifications for hematologic and non-hematologic toxicity and infusion reactions should be independently assessed at each visit. Recommendations for dose modifications for toxicity are provided in Table 8-1 below.

Toxicity Hold Dose % of Full Dose after **Recovery to Grade 0-1** Grade 1 Do not hold dose 100 75 Grade 2 Hold dose until resolution to Grade 0 or 1 Hold dose until resolution to Grade 0 or 1 Grade 3 75 NA Grade 4 Treatment should be discontinued

 Table 8-1
 OBI-888 Dose Modifications for Toxicity

Once the dose has been reduced for toxicity and found to be well tolerated, re-escalation may be permitted at the Investigator's discretion. If a subject requires dose reductions on more than 2 occasions for toxicity related to OBI-888, the subject should discontinue from the study.

All reasons for treatment modifications should be fully explained.

The study drug dose which is not administered within the permitted window period of ± 3 days, must be skipped, and the next dose will be administered as per protocol schedule. Any skipped dose due to safety reason and if medically justified, for OBI-888 treatment related or unrelated reasons, will not be captured as a protocol deviation for this study.

Treatment interruption for more than 2 consecutive doses for related or unrelated reasons may necessitate discontinuation of study treatment.

Treatment interruption for intercurrent non-treatment related adverse events will be at the Investigator's discretion and based on the well-being of the patient. All reasons for treatment interruption and delays should be fully explained. Treatment for hematologic and non-hematologic toxicity may be implemented as clinically indicated according to institutional guidelines. Refer Table 8-2 for therapeutic antiemetic and anti-diarrheal recommendations.

 Table 8-2
 Therapeutic Antiemetic and Anti-Diarrheal Recommendations

| Diarrhea and Abdominal Cramping | Nausea, Vomiting, or Anorexia |
|---|---|
| Dicyclomine: Recommended when the predominant issue is cramping or abdominal pain | 1st line: 5HT3-inhibitors |
| Diphenoxylate/Atropine or/and Loperamide | 2nd-line: Dexamethasone, ideally in combination with a 5HT3-inhibitor. Short term use can be very effective |
| | Other agents: anti-histamines; benzodiazepines; proton pump inhibitors; dopamine antagonists; cannabinoids |

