9.2 Procedures by Study Period

Assessments and study procedures are to be performed as outlined in The Schedule of Assessments, Table 9-1. The PK, ADA, Biomarker, and Glycan Sampling Schedule is provided in Table 9-2 (Part A – Dose Escalation) and Table 9-3 (Part B - Expansion).

The Investigator may at his/her discretion arrange for a patient to have an unscheduled assessment, especially in the case of AEs that require follow-up or an AE considered by the Investigator to be possibly related to the use of study drug. The unscheduled visit page on the eCRF must be completed. Additional visits to follow-up positive ADA may happen after end of study (Table 9-1).

Table 9-1Schedule of Assessments

| Study Procedure | Screening Visit** | Treatment Period | | | | | | |
|--|-------------------|------------------|---|--------|---|---|---------|--|
| Cycle (C) # | - | Cycle 1 | | | | Cycle 2-13 | | |
| Cycle # and Day | | C1D1 | 1D1 C1D8 C1D15 C1D22 | | C1D22 | | | |
| Window period (days) | -28 to -1 days | -1* | ±1 | ±3 | ±3 | ± 3 days | ±7 days | |
| Informed consent ^a | Х | | | | | | | |
| Demographics | Х | | | | | | | |
| Eligibility screening | Х | Х | | | | | | |
| Medical history ^b | X | Х | | | | | | |
| Physical examination ^c | Х | Х | Х | Х | Х | D1 of each Cycle | X | |
| Height, weight ^d | Х | X X X X | | | | D1 of each Cycle | X | |
| Vital signs ^e | X | X X X X | | | Х | D1, D8, D15, D22 of each Cycle | Х | |
| ECOG ^f | Х | | | | | D1 of each Cycle | Х | |
| 12-lead ECG ^g | Х | Х | | | | | | |
| Pregnancy testing ^h | Х | | | | | | X | |
| Tumor biopsy ⁱ | X** | | | | | | | |
| Hematology and Biochemistry ^j | Х | Х | | | | D1 of each Cycle | Х | |
| Coagulation and Urinalysis ^k | Х | Х | | | | | | |
| Drug administration ¹ | | Х | Х | Х | Х | D1, D8, D15, D22 of each 28 day cycle | | |
| Pharmacokinetic sample ^m | | | | See fo | otnote m | and Table 9-2 (Part A) and Table 9-3 (Part B) | | |
| Immunogenicity (ADA) ⁿ | | | | See fo | otnote n | and Table 9-2 (Part A) and Table 9-3 (Part B) | | |
| Biomarkers ^o | Х | | | See fo | otnote o | and Table 9-2 (Part A) and Table 9-3 (Part B) | | |
| Radiology evaluations (CT or MRI) ^p | X | | Q8wk (±1 wk) for the first then Q12wk (±1 wk) th | | Q8wk (±1 wk) for the first 6 months, then Q12wk (±1 wk) thereafter | X | | |
| Concomitant medications | • | • | • | • | • | | | |
| Adverse events | | | | | | | | |

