12.4 Laboratory Assessments

Laboratory assessment samples (Table 12-1) are to be obtained at designated visits as detailed in the Schedule of Assessments (Table 9-1).

| Hematology | Serum chemistry | Urine analysis (dipstick) | |
|---|-------------------------------------|------------------------------|--|
| Hemoglobin | Albumin | Appearance | |
| Hematocrit | Alanine aminotransferase (ALT) | Blood | |
| Platelet count | Alkaline phosphatase (ALP) | pН | |
| Red blood cell (RBC) count | Aspartate aminotransferase (AST) | Protein | |
| White blood cell (WBC) count | Blood urea nitrogen (BUN) or Urea | Glucose | |
| with differential | Bicarbonate | Ketones | |
| | Creatinine | Nitrite | |
| | Creatine kinase | Leukocyte esterase | |
| | Electrolytes (Na, K, Cl, Ca, P, Mg) | Specific gravity | |
| | Glucose | | |
| | Lactate dehydrogenase (LDH) | Urobilinogen | |
| | Total bilirubin | Bilirubin | |
| | Total protein | Microscopic, as | |
| | Uric acid | needed | |
| Coagulation | | | |
| Prothrombin time (PT), International Normalized Ratio | | | |
| (INR) | | | |
| Activated partial thromboplastin time (aPTT) | | | |
| Serum or Urine Pregnancy test: A pregnancy test will be performed on all female patients of | | | |

Table 12-1Laboratory Assessments

child-bearing potential at the screening visit and early termination visit.

The routine safety laboratory testing will be performed at the local laboratory following the lab's guidelines. PK, ADA and biomarkers will be analyzed at a qualified laboratory facility Urine samples will be analyzed by dipstick, and a microscopic analysis will be performed if the results of dipstick indicate abnormalities to be further investigated. All laboratory reports must be reviewed, signed, and dated by the Investigator. Any laboratory test result considered by the Investigator to be clinically significant should be considered an AE (clinically significant AEs include those that require an intervention). Clinically significant abnormal values occurring during the study will be followed until repeat test results return to normal, stabilize, or are no longer clinically significant.

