14.5 Safety Analysis

AEs will be coded according to Medical Dictionary for Regulatory Activities (MedDRA) version 19.0 or higher and assessed for severity using CTCAE version 4.03. AEs will be summarized by system organ class and preferred term and presented in decreasing order of incidence. DLTs will also be summarized by dose and cohort. The incidence of TEAEs (events with onset dates on or after the start of the study drug) will be included in incidence tables. Events with missing onset dates will be included as treatment-emergent. If a patient experiences more than 1 occurrence of the same AE, the occurrence with the greatest severity and the closest association with the study drug will be used in the summary tables. SAEs and AEs causing discontinuation will be tabulated. All AEs will be listed by patient, along with information regarding onset, duration, relationship and severity to study drug, action taken with study drug, treatment of event, and outcome.

Vital signs, ECG data, hematology, serum chemistry, coagulation, and urinalysis parameters from baseline and during study will be examined. Treatment emergent changes in key laboratory parameters will be identified. Clinical laboratory data and vital signs will be summarized for each time point evaluated using descriptive statistics including mean values and mean change from baseline values, as well as numbers of patients with values outside limits of the normal range at each time point.

Summary tables will be provided for concomitant medications initiated prior to study enrollment or during the study period.

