10.8.2 LABORATORY DATA

Tables by visit and by NCI CTC grades (grade 0, grade 1, grade 2, grade 3, grade 4, grade 5) will be presented by laboratory test, where applicable. Worst-post baseline NCI CTC grade for applicable laboratory tests will be also summarized.

Urinalysis results (normal/ abnormal – low/ abnormal - high) will be summarized by visit.

Data listings will be produced for all collected laboratory data, including pregnancy test results.

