14. APPENDIX I. SCHEDULE OF ASSESSMENTS

TABLE 14-1 SCHEDULE OF ASSESSMENTS

Schedule of Assessments

Study Procedure	Screenin g Visit**		Treatment Period						
Cycle (C) #	-	Cycle 1				Cycle 2-13			
Cycle # and Day		C1D 1	C1D 8	C1D C1D1 C1D 8 5 22					
Window period (days)	-28 to -1 days	-1*	±1	±3	±3	±3 days	±7 days		
Informed consent ^a	Χ								
Demographics	Χ								
Eligibility screening	Χ	Χ							
Medical history ^b	Χ	Χ							
Physical examination ^c	Х	Х	Χ	Х	Х	Х	Х		
Height, weight ^d	Χ	Χ	Χ	Χ	Χ	Χ	Х		
Vital signs ^e	Χ	Х	Χ	Χ	Χ	X	Х		
ECOG ^f	Χ					C2D1 only	Х		
12-lead ECG ⁹	Χ	Χ	Χ			C2D1 only	Χ		
Pregnancy testing ^h	Χ						Χ		
Tumor biopsyi	X**								
Hematology and Biochemistry ^j	Х	Х	Х	Х	Х	Every 2 weeks (D1 and D15 of each Cycle)	Х		
Coagulation and Urinalysis ^k	Х	Х				Every 2 cycles, D1 (C2 C4, C6, C8, C10, C12)	Х		
Drug administration ^l		Х	Χ	Х	Χ	D1, D8, D15, D22 of each 28 day cycle			
Pharmacokinetic sample ^m		See	footn	ote m	and 7	Table 14-2 (Part A) and Table (Part B)	e 14-3		
Immunogenicity (ADA) ⁿ		See	footr	ote n	and T	able 14-2 (Part A) and Table (Part B)	14-3		
Biomarkers ^o	Х	See	footr	ote o	and T	able 14-2 (Part A) and Table (Part B)	: 14-3		
Radiology evaluations (CT or MRI) ^p	Х		End of every 2 cycles			х			
Concomitant medications	Х	Х	Х	Х	Х	X	Х		
Adverse events		Х	Χ	Χ	Χ	X	Χ		

EOS/ET - End of Study/Early Termination. EoS Visit is the safety follow-up visit, conducted

Review Status: Final Version: 2.0

Version Date: 02JUN2022

28±7 days after the last OBI-888 dose. ET visit lab assessments will be conducted for patients discontinuing study treatment, if last available tests are before 2 weeks.

*The - 1 day window (1 day prior) for C1D1 is for safety laboratory assessments. Blood can be drawn 1 day prior to initiation of study drug infusion on C1D1. Safety laboratory results should be available and reviewed by the Investigator prior to the OBI-888 administration.

** All patients are required to provide a tumor biopsy sample, unstained slides (preferred) or a FFPE tissue block at the initiation of screening visit for screening of Globo H overexpression and confirmation for eligibility of patients for Part B. Patients with a confirmed and documented Globo H H-score of ≥ 100 are eligible for the study, and will subsequently enter the 28-day screening period to complete the remaining screening procedures.

Footnotes:

- a. Informed consent to be obtained before any other study procedures are performed.

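### Protocol Table 9-1 schedules no post-dose blood count before Cycle 2 Day 1, so it does not support sections 8.3, 6.2 and 14.5; SAP Appendix I carries a different laboratory schedule and does not declare the difference

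*Protocol*

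**What the plan says.** **Dosing and toxicity assessment.** Protocol 8.2.2: "OBI-888 will be administered as an IV infusion on Days 1, 8, 15, and 22 of each 28-day cycle". Protocol 8.3: "Dose modifications for hematologic and non-hematologic toxicity and infusion reactions should be independently assessed at each visit".

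**DLT criteria.** Protocol 6.2 counts Grade 4 neutropenia, Grade 4 thrombocytopenia and Grade 3 thrombocytopenia with bleeding, and adds: "The DLT evaluation period is the first cycle; 28 days from start of study treatment".

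**Protocol laboratory schedule.** Protocol 12.4 sends the reader to one table: "Laboratory assessment samples (Table 12-1) are to be obtained at designated visits as detailed in the Schedule of Assessments (Table 9-1". There, the row "Hematology and Biochemistry" is marked at screening, C1D1, Day 1 of each later cycle and EOS/ET. The cells for C1D8, C1D15 and C1D22 are blank. Footnote j places the draw before the infusion, so the C1D1 value is a baseline value. Coagulation and urinalysis are marked only at screening and C1D1, and footnote k makes these pre-infusion too.

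**SAP laboratory schedule.** SAP Table 14-1 marks hematology and chemistry at all four Cycle 1 visits, then "Every 2 weeks (D1 and D15 of each Cycle", and at EOS/ET. Coagulation and urinalysis appear at screening, C1D1, Day 1 of every second cycle and EOS/ET.

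**Planned analyses.** Protocol 14.5 says that "hematology, serum chemistry, coagulation, and urinalysis parameters from baseline and during study will be examined". SAP 10.8.2 says "Worst-post baseline NCI CTC grade for applicable laboratory tests will be also summarized", and also summarises urinalysis by visit.

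**The concern.** Laboratory abnormalities by CTCAE grade are a primary endpoint, and the worst-grade summary is one of the laboratory outputs kept for the abbreviated report. A worst grade is a maximum over draws, so it tends to rise with the number of draws. Two schedules that differ in density can give different worst-grade tables for the same underlying toxicity.

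The DLT criteria have a related problem. A silent Grade 4 neutropenia or thrombocytopenia can be identified only from a count, and the Safety Review Committee is to judge DLTs from adverse events and laboratory toxicities after Cycle 1 (protocol 14.6). A schedule with no post-dose count in that cycle does not supply the data that the criterion needs.

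The SAP says that it covers protocol version 5.0, and protocol section 14 says that the SAP prevails where the two differ. SAP section 11, which lists departures from the protocol, does not mention the laboratory schedule. A reader of the worst-grade table therefore cannot tell how often each patient was sampled.

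**Working it through.** The plan states no figure on this point, so there is none to reproduce. The check counts scheduled draws and then asks what the counts imply.

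**1. Scheduled draws.** The inputs are the hematology and chemistry rows of Protocol Table 9-1 and SAP Table 14-1, and infusions on Days 1, 8, 15 and 22. Both tables run to Cycle 13.

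| | Table 9-1 | SAP Table 14-1 |
|---|---|---|
| Post-dose draws after C1D1 and before C2D1 | 0 | 3 |
| Post-dose draws through C2D1 | 1 | 4 |
| Infusions with a same-day count, Cycle 1 | 1 of 4 | 4 of 4 |
| Same, each later cycle | 1 of 4 | 2 of 4 |
| Same, 13 cycles | 13 of 52 | 4 + 12 × 2 = 28 of 52 |

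Infusions without a scheduled count are 39/52 = 75% under Table 9-1 and 24/52 = 46% under the SAP schedule. C2D1 falls on nominal Day 1 + 28 = Day 29, one day past the DLT window. Its ±3-day window can bring it to Day 26.

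**2. Chance that a scheduled draw catches an episode.** Let an episode last L days, with onset uniform over the cycle and draws every D days. The chance is min(1, L/D). D is 28 under Table 9-1. Under the SAP schedule D is 7 in Cycle 1, counting the Day 29 draw, and 14 later. If only the draws on Days 8, 15 and 22 count, the Cycle 1 chance is 3 × min(L, 7)/28. The durations are assumptions; neither document gives any.

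| Assumed L | Table 9-1 | SAP, Cycle 1, with Day 29 | SAP, Cycle 1, Days 8–22 only | SAP, later cycles |
|---|---|---|---|---|
| 3 days | 3/28 = 11% | 3/7 = 43% | 9/28 = 32% | 3/14 = 21% |
| 7 days | 7/28 = 25% | 100% | 21/28 = 75% | 7/14 = 50% |
| 14 days | 14/28 = 50% | 100% | 21/28 = 75% | 100% |

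In Cycle 1 the Table 9-1 column depends wholly on the C2D1 draw. If that draw falls on nominal Day 29, detection inside the 28-day window is 0%. All figures ignore unscheduled and symptom-driven draws.

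**3. Coagulation and urinalysis.** Table 9-1 schedules none after the first dose, and its EOS/ET cell is blank. Protocol 14.5 and SAP 10.8.2 nevertheless expect values during the study. Other routes are the footnote on ET laboratory tests when the last results are more than two weeks old, protocol 7.3 (early withdrawals complete all assessments), and unscheduled assessments under 9.2.

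**4. Are the blanks an extraction fault?** Probably not. The vital-signs and drug-administration rows of Table 9-1 keep their Cycle 1 marks, and no footnote adds draws.

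**The case against.** Several points against the concern carry weight.

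- **Section 8.3 does not say that a count is required.** It calls for assessment at each visit. On the strictest reading SAP Table 14-1 also falls short, with no counts on Days 8 and 22 from Cycle 2. This stands, and is a reason to reconcile 8.3 with whichever table applies rather than to prefer one table.
- **The SAP appendix may simply be out of date.** It keeps a 13-cycle limit that the protocol's drug-administration footnote lacks, refers to tables under numbers they do not carry, and sits beside a PK plan based on protocol version 4.0. This is plausible. It would explain the mismatch but not remove it, because the SAP claims to cover version 5.0.
- **SAP Appendix I derives no laboratory result.** Data are analysed by eCRF visit, and CTC grades by visit are shown beside worst grade. True, but the worst-grade summary still depends on how many draws each patient had.
- **Unscheduled assessments are allowed, and symptomatic events prompt tests.** This stands, and the detection figures leave such draws out.

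A reader might go further and infer that Parts A and B are not comparable because Part A was sampled weekly and Part B monthly. The documents do not support that. Each gives a single schedule for both parts. Three Part B patients were enrolled by March 2020, before version 5.0 of 08 May 2020, so a change by version would not follow the A/B split. SAP 10.1 gives Part A and Part B separate totals and specifies no pooled 20 mg/kg laboratory table.

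Nor do the documents show that DLTs were missed. SAP 10.7.1 places the DLT period in Part A, which was complete before version 5.0 and may have had denser sampling. The two inferences also pull apart: if Part A had weekly Cycle 1 counts, the Table 9-1 gaps did not affect its DLT evaluation; if it followed Table 9-1, a Part A versus Part B sampling difference has no basis.

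**Conclusion.** The inconsistency is real and should be corrected. Table 9-1 does not support the each-visit assessment in 8.3, the cytopenia criteria in 6.2 or the on-study coagulation and urinalysis review in 14.5. SAP Table 14-1 contradicts it without acknowledgement.

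The size is 0 versus 3 scheduled post-dose counts before C2D1, and 25% versus 54% of infusions over 13 cycles with a same-day count. The detection figures illustrate the possible effect and rest on assumed durations and uniform onset.

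What follows is a risk: toxicity may be under-detected under Table 9-1, and worst grade may differ between patients sampled on different schedules. Actual under-detection is not established, because the documents do not say which schedule applied to whom. It would also be too strong to say that no on-treatment coagulation or urinalysis data exist; none is scheduled after the first dose under Table 9-1. I take the current protocol to be version 5.0, which its March 2020 data summary fits. Nothing here says which schedule is clinically right.

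**What to change.** 1. Reconcile Protocol Table 9-1, sections 8.3, 6.2 and 14.5, and SAP Appendix I. The sponsor decides which schedule stands.
2. In the SAP, state which laboratory schedule applied to which patients, by protocol version if that is how it changed, and list the difference in section 11.
3. Report the number of post-baseline draws per patient beside the worst-grade table in SAP 10.8.2.
4. If patients sampled on different schedules are ever compared or pooled, also show worst grade from the post-baseline Day 1 draws common to both schedules (Cycle 2 onward), next to the all-draws version.
5. State that under Table 9-1 no coagulation or urinalysis is scheduled after the first dose, so such values would come only from early-termination or unscheduled assessments.

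The cost is a document correction and one added summary of draw counts, with a second worst-grade table only if item 4 applies. The analysis changes need no new sampling.

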8.3.1 Infusion Reactions

Signs/symptoms of infusion reactions may include: allergic reaction/hypersensitivity (including drug fever); arthralgia (joint pain); bronchospasm; cough; dizziness; dyspnea (shortness of breath); fatigue (asthenia, lethargy, malaise); headache; hypertension; hypotension; myalgia (muscle pain); nausea; pruritic/itching; rash/ desquamation; rigors/chills; sweating (diaphoresis); tachycardia; tumor pain (onset or exacerbation of tumor pain due to treatment); urticaria (hives, welts, wheals); and vomiting.

In the event of an infusion reaction, additional serum/plasma samples may be drawn at the time of the event to evaluate drug concentration and anti-drug antibody, as well as to assess levels of cytokines and/or other markers of inflammation.

Prophylactic Measures

Prior to dosing with OBI-888, patients should receive prophylactic treatment for infusion reactions consisting of acetaminophen orally and diphenhydramine (or equivalent) orally or IV 30 to 60 minutes prior to infusion of OBI-888 (recommended doses are: acetaminophen 650 mg, diphenhydramine 50 mg). If an alternative premedication regimen is thought to be required, Sponsor approval should be sought.

For patients who experience an infusion reaction despite initial premedication, additional prophylactic treatment may be added prior to subsequent doses, including an H2 blocker such as ranitidine, and/or corticosteroids.

Prophylactic treatment for infusion reactions may be withheld at the Investigator's discretion if no infusion reactions were observed with the first cycle of treatment.

Management of Infusion Reactions

In the event of an infusion reaction, the OBI-888 infusion should be interrupted and medical therapy administered according to institutional standard of care which, depending upon the severity of the event, may include but should not be limited to use of H1 and H2 inhibitors, and corticosteroids.

Patients who experience a Grade 1 or Grade 2 infusion reaction may resume the infusion of drug at a reduced infusion rate (30% to 50% slower than initial rate) on the same day following appropriate medical management. If the 4-hour window from product reconstitution to completion of infusion will be exceeded (Appendix 1), new drug may be prepared to administer the remainder of the planned dose.

Patients who experience a Grade 3 infusion reaction may be retreated at the discretion of the Investigator at the next scheduled treatment. Such patients should receive additional prophylactic medication that may include a corticosteroid, and the duration of infusion may be increased.

OBI-888 should be permanently discontinued in patients who experience a life-threatening (Grade 4) infusion reaction.

